Weill Cornell Medicine

IRB Protocol Number: 1706018342
Clinicaltrials.gov ID: NCT03467763

Protocol and Statistical Analysis Plan: 07/09/2018

Title: Trial of an intervention to Improve Metformin Persistence and Adherence

Coordinating Center: Weill Cornell Medicine, Department of Medicine

Primary Investigator: [name].

Coinvestigator: [name].

Protocol Version	IRB Approval
Version 1	01/29/2018
Version 2	07/09/2018

Study Overview:

This protocol outlines the design for a randomized controlled trial entitled, "Trial of Restarting and Tolerating Metformin (TreatMet)". Metformin is a safe and effective first-line drug for type 2 diabetes that is also widely recommended for weight loss and diabetes prevention. But, metformin is associated with gastrointestinal and other side effects which prevent its use in 10-20% of patients and appear to limit the usable dose in others. This study is an N-of-1 trial design that will recruit 20 previously metformin-intolerant patients for re-challenge with metformin in a double-blind scenario. In this setting, 'intolerant' means either unable to take metformin at all, or unable to increase the dose past 1,000 mg despite the treating physician's recommendation to do so. Patients will be assigned to take their baseline medication regimen plus 2 weeks of 250 mg per day of metformin extended release, followed by 500 mg metformin XR, 750 mg, and 1,000 mg metformin XR with each treatment period separated by a 2-week course of placebo. Initial treatment, placebo or metformin XR, will be decided randomly. At the end of each two-week treatment period, participants will complete questionnaires assessing overall satisfaction with the medication, gastrointestinal symptoms, and adherence. Six months after the conclusion of the intervention, follow-up will establish if patients are continuing metformin at a higher dose than upon entry to the trial. This trial has two aims. First, to test the hypothesis that medication satisfaction will be the same during periods of placebo treatment and during periods of treatment with the active drug. The second aim is to test the hypothesis that > 30% of metformin-intolerant patients in an N of 1 crossover trial are able to tolerate higher-dose metformin at 6-months.

Relevant Scientific Background:

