There are over 14 million unique prescriptions for metformin in the U.S annually, and it is widely regarded as a very safe medication for the treatment of type 2 diabetes mellitus; though side effects do occur. The most frequent adverse events attributable to metformin are primarily gastrointestinal, including nausea, diarrhea, and GI upset. Metformin contains a black-box warning for lactic acidosis, however cases of this occurring nearly are nearly non-existent. One study (Salpeter) found, "There is no evidence to date that metformin therapy is associated with an increased risk of lactic acidosis or with increased levels of lactate compared with other antihyperglycemic treatments if the drugs are prescribed under study conditions, taking into account contraindication".² Furthermore, risk of hypoglycemia is near zero with metformin. The package insert for metformin produced by the FDA states, "hypoglycemia does not occur in patients receiving metformin alone under usual circumstances of use, but could occur when caloric intake is deficient, when strenuous exercise is not compensated by caloric supplementation, or during concomitant use with other glucose-lowering agents (such as sulfonylureas) or ethanol".

From a pragmatic point of view, it has been proposed that for patients who are strongly motivated to use a medication but experience subjective discomfort when using it, an n-of-1 placebo-controlled trial can be a therapeutic intervention. For patients who are having difficulty assessing whether their quality of life is worsened by exposure to a drug like metformin or a statin, undergoing a placebo-controlled double-blinded crossover study and finding that they cannot distinguish between the two could reduce concerns about purely subjective, placebo-driven side effects, and allow patients to use the drug without experiencing those effects. Conversely, if side effects are clearly reproducible with exposure to drug over placebo, patients and their providers could confidently conclude that the drug really is not tolerable for that patient. This idea has been developed to a limited extend in statin use, but has not been applied to diabetes treatments.

Methods:

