Patients will be recruited at Weill Cornell Medicine and will be eligible if they have a diagnosis diabetes, pre-diabetes, or obesity, previously attempted to take metformin for one of these indications, and have a history of intolerance to metformin. Intolerance may manifest either as the inability to take metformin at all, or the inability to titrate the dose past 1,000 mg due to side effects. Intolerance will be defined based on the treating

physician's assessment that a history of metformin intolerance (defined as the inability, due to side effects, to use metformin at the otherwise medically appropriate dose) exists, confirmed by the patient's recollection of the same history .

Subject will be recruited that currently have a diagnosis of diabetes, pre-diabetes, or obesity, and possible related comorbidities, but who are ambulatory, independent, and neither seriously nor terminally ill.

Electronic medical records will be reviewed for patients who have been prescribed metformin hydrochloride and for whom the medical record indicates that metformin intolerance occurred and limited the patient's ability to take metformin.

Physicians involved in the clinical trial will identify eligible patients. Once identified, the physician will approach the patient in the clinic at their next appointment and discuss participation in the study. With the permission of other providers at WCMC, such as primary care providers, physicians involved in TreatMet or other study personnel in TreatMet may contact patients by telephone to invite them to participate in this study. Physicians will receive an email, or personal contact inquiring whether they are willing to give the investigators permission to contact specific patients, or to contact patients themselves. Only after obtaining physician approval, patients will be contacted via telephone to invite them to participate in TreatMet. Patients will be contacted during normal office hours. If a patient declines participation, they will not be contacted again. If patients do agree, an in-person meeting for written informed consent will be scheduled. Patients are free to opt-out at any point in this process.

Study Design:

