This trial is a self-controlled, double blind crossover study enrolling patients with a clear history of metformin intolerance. Intolerance is defined here as the inability, despite the recommendations of the treating physician, either to take metformin at all, or to increase daily metformin dose beyond 1,000 mg. The study intervention is the addition of 250 mg, 500 mg, 750 mg, and 1,000 mg of metformin daily, to the patient's existing regimen. Up to twenty patients will be enrolled for ten months. For one two-week block they will have 250 mg of metformin extended-release added to their existing regimen, followed by two-week blocks of 500 mg, 750 mg, and 1,000 mg metformin XR, each separated by two-week periods of placebo. The order of treatment assignments will be double-blinded and randomized, except that the 250 mg, 500 mg, 750 mg, and 1,000 mg blocks will always occur in order, smallest to largest.

Primary Objectives:

For aim 1 of this study, the primary objective is to test the hypothesis that patients will have similar treatment satisfaction on metformin and on placebo. The primary outcome of this portion of the study will be the results of the Treatment Satisfaction Questionnaire for Medication. For aim 2 of this study, the primary objective is to test the hypothesis

that > 30% of the patients enrolled in this study are able to tolerate higher-dose metformin at 6 months.

Secondary Objectives:

For aim 1, the secondary objectives are to test the hypotheses that scores on a gastrointestinal symptom questionnaire are not significantly different between placebo and intervention periods; that adherence is not significantly different between periods; and that the answer to the question 'Were you taking placebo or metformin for the past two weeks' is correct no more often than would be predicted by chance.

Statistical Considerations:

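### Does the placebo-or-metformin guess question lack a right answer for patients who already take metformin?

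*Combined protocol and SAP*

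**What the plan says.** The question appears once, under Secondary Objectives: "Were you taking placebo or metformin for the past two weeks". The hypothesis is that the answer "is correct no more often than would be predicted by chance". The plan states no scoring key, chance level or test for it. The Study Overview says that after each block "participants will complete questionnaires assessing overall satisfaction with the medication, gastrointestinal symptoms, and adherence"; the guess is not on that list.

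Two other features matter.

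- **Who is eligible.** Methods: "Intolerance may manifest either as the inability to take metformin at all, or the inability to titrate the dose past 1,000 mg". The second group may be taking metformin at entry. The follow-up endpoint in the Study Overview allows for this: "follow-up will establish if patients are continuing metformin at a higher dose than upon entry to the trial".
- **What happens to the existing regimen.** It continues. Study Overview: "Patients will be assigned to take their baseline medication regimen plus 2 weeks of 250 mg per day of metformin extended release". Study Design: "For one two-week block they will have 250 mg of metformin extended-release added to their existing regimen". No washout of a patient's own metformin is stated.

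**The concern.** A patient on their own metformin takes it in placebo blocks too. Read word for word, the question does not say whether it means the blinded study medication or everything swallowed in the past two weeks. Such a patient could truthfully answer *metformin* every time, whatever the blinded capsules contained and whether or not they could tell.

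If those answers are scored against the block's assignment, the patient is right in the metformin blocks and wrong in the placebo blocks, and contributes nothing about recognition. That dilutes real recognition in the other patients and moves the result towards the trial's own hypothesis. If the answers were scored against everything taken, the same patient would be right every time, and the trial could appear to show recognition that does not exist.

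The item has some weight. It is the only listed outcome that asks patients directly to tell drug from placebo. The background section gives that experience as the route to benefit: "finding that they cannot distinguish between the two could reduce concerns about purely subjective, placebo-driven side effects".

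**Working it through.** The documents give no figure for this question, so there is no stated number to reproduce. The aim 1 sample size of 16 concerns the satisfaction score and does not enter here.

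**Step 1: is there an answer key?** Study Design describes a double-blind crossover made up of two-week blocks, each assigned to placebo or to a metformin dose. The guess question closes a sentence whose first item compares symptom scores under placebo with those under study drug. A patient who takes their own metformin knows it, so asking about those tablets would test nothing. A hypothesis about chance also makes sense only if the key varies between blocks. Each point leads to the block's assignment as the key. In addition, a background user in a placebo block is taking both, so *placebo* is as literally true as *metformin*. The literal reading does not force a fixed answer.

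**Step 2: what does a fixed *metformin* answer score?** There are four metformin blocks. The number of placebo blocks is not stated, so take three, four or five:

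- seven blocks: 4/7 = 57%
- eight blocks: 4/8 = 50%
- nine blocks: 4/9 = 44%

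**Step 3: how many such patients?** Number = 20 × share on background metformin × share of those who answer literally. Neither share is given. Assuming 25–75% and 25–100%:

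- low end: 20 × 0.25 × 0.25 = 1.25
- high end: 20 × 0.75 × 1.00 = 15

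**Step 4: effect when scored by assignment.** Assumptions: 20 patients, eight blocks, independent guesses with 65% correct in the other patients, literal responders fixed at 4 of 8, and a one-sided 5% one-sample t-test of patient scores against 4 of 8. With L literal responders, overall percent correct = [L × 50 + (20 − L) × 65] / 20. Power is by simulation.

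| L | Overall % correct | Power |
|---|---|---|
| 0 | 65.0 | 0.98 |
| 2 | 63.5 | 0.97 |
| 3 | 62.8 | 0.96 |
| 5 | 61.3 | 0.94 |
| 10 | 57.5 | 0.81 |
| 15 | 53.8 | 0.48 |

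The loss depends on how well the others recognise drug. With L = 0, 5, 10 and 15, power is about 0.80, 0.68, 0.52 and 0.26 at 60% recognition, and 1.00, 1.00, 0.96 and 0.70 at 70%.

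**Step 5: effect when scored literally.** With nobody recognising anything and literal responders credited with 8 of 8, the false-positive rate rises from 0.05 to 0.10, 0.18, 0.32 and 0.70 with 1, 2, 3 and 5 such patients. These are the striking figures. They need an analyst who holds the allocation list to mark *metformin* correct for an assigned placebo block. Nothing in the documents suggests that rule, and it would leave no drug-placebo contrast to compare with chance.

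**Step 6: would misreading be visible?** Partly. The 6-month endpoint requires the dose at entry, so background users can be identified. Eight identical *metformin* answers would arise from fair, independent guessing with probability (1/2)^8 = 1/256, about 0.4%. A run of this kind in a background user is a flag, though not proof, since a patient may sincerely believe that every block was active.

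**The case for a change.** The best case for a change is that inferring the key settles only the scoring; it does not settle what the patient understood. Under assignment scoring, a patient who misreads the question adds no information and moves the result towards the hypothesis the trial hopes to support. Once collected, a literal *metformin* and a sincere guess of *metformin* cannot be told apart with certainty, while a few added words on the form would cost nothing. At 60% recognition, five such patients would take power from about 0.80 to 0.68, which is not trivial.

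Much of this stands. The direction of the bias is right, the wording is loose, and naming the study medication on the form would do no harm. What does not stand is the claim that no right answer exists, or that literal scoring is a live possibility.

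The remaining harm depends on how many people in a blinded add-on trial would take the question to be about their own prescription. The documents do not give that rate. They quote the question inside an objective and do not reproduce the form, so any instruction that goes with it cannot be checked.

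The unstated number of blocks, what exactly is randomised, and the clustering of guesses within a patient are separate matters. They would arise even if no patient took metformin at entry, so they add nothing to this point.

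**Conclusion.** No change to the plan follows. This is missing detail that analysts would fill sensibly: score each guess against the treatment assigned for that block, and look at the answers by metformin use at entry. The question is loosely worded for background users, but its intended meaning is clear from the design and the surrounding text.

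Under that key, up to 5 of 20 patients answering *metformin* throughout cost about 0.04 of power (0.98 to 0.94) at 65% recognition, and about 0.12 (0.80 to 0.68) at 60%. At 65%, power falls to 0.81 only when half the sample misreads. All of this assumes eight blocks, independent guesses and a one-sided 5% t-test, none of which the plan states, and the rate of misreading is unknown. The effect is confined to one of three secondary hypotheses under aim 1. The satisfaction outcome, the 6-month outcome and the sample size do not depend on it.

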With respect to sample size for aim 1, by Lehr's approximation, a sample size of 16 would be needed to identify a 1 standard deviation difference in the mean score on the Medication Treatment Satisfaction Questionnaire. The target sample size is 20 patients to account for possible patient dropout. With respect to sample size for aim 2, by Lehr's approximation, a sample size of 20 provides 95% confidence intervals of approximated +/- 20% around most reported percentages. If the reported rate of success in increasing metformin dose is 30%, the 95% confidence interval around that estimate will range from 10% to 50%. If the reported percentage is 0%, the 95% confidence interval will be approximately 0-15%. We think these are sufficiently precise estimates to help clinicians decide whether n-of-1 clinical trials are a useful intervention for overcoming metformin intolerance.

Inclusion/ Exclusion Criteria:

Patients will be eligible if they are between the ages of 18 and 100. Patients will be recruited in an outpatient setting. Subjects will be enrolled regardless of gender, though a 50:50 ratio of male to female subjects is desirable.

Patients will be ineligible if they have a contraindication to metformin (ie, advanced renal or liver disease, a history of lactic acidosis attributed to metformin, or advanced heart failure). Pregnant women will be excluded from this study due to risk of confounding; pregnant women frequently have nausea and vomiting, changing over time, which if included may invalidate the results of the study.

Assessing Safety and Efficacy:

No data will be collected systematically to monitor safety or efficacy, only tolerability. However, the gastrointestinal symptom questionnaire will serve to quantify gastrointestinal adverse events every 2 weeks. Patients will be educated on potential side effects and risks of metformin and encouraged to both stop the medication and contact the investigators if they experience intolerable side effects or any severe adverse reactions.

Interim and Complete Stopping Rules:

Due to the small sample size, short duration, and limited risks of this study, statistical stopping rules are not specified. Patients are encouraged to speak with their physicians and study coordinators regarding any medication-associated adverse events that may occur as a result of participation in this study.

Adverse Events Collection:

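### The guess objective makes the null its hypothesis, with no bound and no analysis by dose, so a non-significant result pooled over periods would read as support, however imprecise

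*Combined protocol and SAP*

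**What the plan says.** Secondary Objectives (combined protocol and SAP) lists three hypotheses for aim 1. It opens: "the secondary objectives are to test the hypotheses that scores on a gastrointestinal symptom questionnaire are not significantly different between placebo and intervention periods". Adherence is worded the same way. The third is that the patient's answer on whether the last two weeks were placebo or metformin "is correct no more often than would be predicted by chance".

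Neither that section nor Statistical Considerations gives a test, significance level, upper bound, unit of analysis, definition of chance or breakdown by dose for this objective. The sample size rests on the satisfaction score and on the aim 2 interval: "The target sample size is 20 patients to account for possible patient dropout".

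On the sequence, Study Overview says "Initial treatment, placebo or metformin XR, will be decided randomly", and Study Design has the four metformin blocks in ascending dose, "each separated by two-week periods of placebo". The number of periods is not stated. Study Design adds "Up to twenty patients will be enrolled for ten months", and Study Overview places follow-up "Six months after the conclusion of the intervention".

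**The concern.** A hypothesis of no discrimination cannot be supported by failing to reject it, unless the plan also says how much discrimination would be too much and shows that the data exclude it. Here the smaller and noisier the trial, the more easily the hypothesis survives, so the error runs towards what the investigators expect to find.

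The objective is also worded once for all periods. The 1,000 mg block, the highest dose added, contributes one answer in about eight, so recognition confined to that dose is diluted by the other answers.

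The result would be read closely. The Background argues that patients "finding that they cannot distinguish between the two could reduce concerns about purely subjective, placebo-driven side effects". A report that patients guess no better than chance would be taken as evidence for that premise, even if some patients, or all of them at the top dose, could tell.

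**Working it through.** **The plan's own figures.** None is given for this objective. The nearest ones reproduce:
- 30% of 20 patients: 0.30 ± 1.96 × √(0.30 × 0.70 / 20) = 0.30 ± 0.20, the stated 10% to 50%.
- 0 of 20: 3/20 = 15%, the stated upper limit.
- Lehr for 1 SD: 16/1² = 16.

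**Inputs from the documents.** Up to 20 patients; 16 as a dropout case; four metformin blocks, with 1,000 mg occurring once.

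**Assumptions not in the plan.** Eight periods (four placebo), one answer per period, independent 50% guessing outside the 1,000 mg block, one-sided 5% test. Follow-up of six months plus seven, eight or nine two-week periods comes to 9.2, 9.7 or 10.1 months, so the stated ten months does not settle the count.

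**Scenario.** Every patient recognises the 1,000 mg block. Pooled rate = (1 + 7 × 0.5)/8 = 56.25%.

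**Precision.** Exactly half correct, 80/160, has an exact 95% interval of 42.0% to 58.0%. The scenario lies inside it.

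**Pooled test.** The cut-off is 91/160 (size 0.048). Detection = P(20 + Bin(140, 0.5) ≥ 91) = 0.466, so the scenario is missed in 53% of trials. Variants:

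| Patients × periods | Scenario rate | Cut-off | Missed |
|---|---|---|---|
| 20 × 8 | 56.25% | 91/160 | 53% |
| 20 × 7 | 57.1% | 81/140 | 54% |
| 20 × 9 | 55.6% | 102/180 | 59% |
| 16 × 8 | 56.25% | 74/128 | 61% |

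**Dependence on answering habit.** Let q be the chance of saying metformin outside the 1,000 mg block (three metformin and four placebo periods). Pooled rate = (1 + 3q + 4(1 − q))/8 = (5 − q)/8.

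| q | Rate | Missed (20 × 8) |
|---|---|---|
| 0 | 62.5% | 0% |
| 0.2 | 60.0% | 12% |
| 0.5 | 56.25% | 53% |
| 0.8 | 52.5% | 92% |

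**Pairing by dose.** Pair the 1,000 mg block with a neighbouring placebo period and compare patients right on both with patients wrong on both. With no recognition and a fixed lean q, the two probabilities are q(1 − q) and (1 − q)q. They are equal, so a lean alone does not look like recognition. With 90% recognition, and the placebo answer right half the time, they are 0.45 and 0.05. The exact one-sided sign test in 20 patients then has 79% power at 5%, 58% at 1.25% (four doses sharing the 5%), and 67% at 5% with 16 patients. The pooled test has 34% power for the same 90% recognition.

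**Would an overall bound be enough?** Under the full-recognition scenario, the upper limit of a 95% t-interval on 20 patient means falls below 60% in 16% of simulated trials and below 65% in 61% (100,000 simulations). With no ability and independent answers, the figures are 67% and 95%. If each patient's answers are all right or all wrong, as when everyone answers in strict alternation, they are 13% and 25%.

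**The case against.** **No decision rule is stated.** This is true, so treating non-significance as support is an inference. It is the natural one, because the two neighbouring hypotheses are expressed as absence of significance.

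**A 50% result does not in general leave universal recognition open.** A reader might infer that it does. That holds only for the rate pooled over periods. At 1,000 mg alone, 10/20 correct has an upper limit of 73%, which excludes 100%. Over the metformin blocks, 40/80 has an upper limit of 61.4%, which excludes the scenario's (1 + 3 × 0.5)/4 = 62.5%. The plan does not forbid such a table; it does not specify one either.

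**The 53% rests on coin-flip guessing.** This stands. Patients who say placebo whenever they notice nothing would be detected every time, while a lean towards metformin makes matters worse. The documents do not show which applies.

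**Independent answers are not the most precise case.** A reader might take 42% to 58% as the narrowest possible interval. It is not: with eight alternating periods, a patient who gives the same answer throughout scores exactly 4/8, so a lean can narrow it.

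**The period count matters at the edge.** Under the scenario, the probability of half or fewer correct is 0.054 with eight periods but 0.041 with seven. At one-sided 5%, a pooled 50% result would therefore exclude the scenario if there are seven.

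**The Background concerns individual patients.** This is fair. The group guess rate bears on that premise but is not the whole of it, and the documents do not support saying that the rationale falls with it.

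**Conclusion.** The concern holds in a limited form. As worded, the objective lets a non-significant pooled result stand as support, with no bound, no interval and no look at the dose where recognition is most plausible. Under the stated assumptions, the pooled test misses universal recognition of the 1,000 mg block in 53% to 61% of trials across the period counts and the dropout case examined. Under other answering habits the figure runs from 0% to 92%. These figures illustrate the weakness; they do not predict the trial's result.

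The point is worth correcting but not critical. It concerns one secondary objective and leaves both primary outcomes and the sample size untouched.

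**What to change.** 1. Reword the objective as estimation: the proportion of correct answers with a 95% confidence interval, the patient being the unit. State that a non-significant result will not be reported as inability to tell.
2. Report the answers by dose, pairing each metformin block with a neighbouring placebo period as above, and say in advance whether the four doses share the 5%.
3. State the permitted sequences and the number of periods. If assignments alternate from a random start, one draw fixes all of a patient's assignments, which is why the patient is the safer unit; the statement in Study Design that the order is randomised could also be read differently. With seven periods there are three placebo periods for four metformin blocks, so the pairing rule must cover that case.
4. If a conclusion of inability to tell is wanted, fix and justify an upper bound beforehand and apply it by dose as well as overall. An overall bound alone does not cure the problem.

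Cost: some added analysis text and a multiplicity decision. No new data are needed, provided that the question is asked after every period, as its wording implies. The downside is that, with 20 patients, a conclusion of inability to tell may be out of reach; the estimate would then be reported without it. No dose or schedule changes.

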Adverse events that may cause termination or dropout of a subject include hypoglycemia, lactic acidosis, and severe gastrointestinal effects including severe nausea, vomiting, and diarrhea.

Metformin has a well-established safety profile in this clinical setting and no active monitoring for adverse events is planned. Patients who are using diabetes drugs associated with hypoglycemia (sulfonylurea, insulin, or meglitinide) will be advised of the potential for metformin to increase risk of hypoglycemia by potentiating the action of those drugs, and to immediately report any occurrence of hypoglycemia both to the study team and to their regular physician

Adverse events will be graded according to the "Common Terminology Criteria for Adverse Events (CTCAE) v4.0" scale produced by the United States Department of Health and Human Services and the National Institutes of Health. The CTCAE scale rates potential adverse events on a scale from 1 to 5, and is a commonly accepted method of grading adverse events. All adverse events will be recorded on the Office of Research Integrity's "Adverse Event & IND Safety Reporting Cumulative Table". We will report all required adverse events and incidents to NYPH-WCM Patient Services, Risk Management, and/or the Department of Health.

In addition to the IRB, all adverse events recorded during this trial will be reported to [name], and [name].

¹ Joy TR, Monjed A, Zou GY, Hegele RA, McDonald CG, Mahon JL. N-of-1 (Single-Patient) Trials for Statin-Related Myalgia. *Annals of Internal Medicine*. 2014;160(5):301-310

² Salpeter SR, Greyber E, Pasternak GA, Salpeter EE. Risk of fatal and nonfatal lactic acidosis with metformin use in type 2 diabetes mellitus. *Cochrane Database Syst Rev*. 2010;2010(4):Cd002967.

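### Aim 1 has no score for a patient who leaves mid-block because of side effects, so a true metformin effect would be understated toward the hypothesised similarity

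*Combined protocol and SAP*

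**What the plan says.** All references are to the combined protocol and SAP.

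- **Sample size (Statistical Considerations).** By Lehr's approximation, "a sample size of 16 would be needed to identify a 1 standard deviation difference in the mean score". Then: "The target sample size is 20 patients to account for possible patient dropout". Nothing else is said about how dropout affects aim 1.
- **Timing of scores (Study Overview).** "At the end of each two-week treatment period, participants will complete questionnaires assessing overall satisfaction with the medication, gastrointestinal symptoms, and adherence". No other time point is given for these questionnaires.
- **Stopping (Assessing Safety and Efficacy).** Patients are "encouraged to both stop the medication and contact the investigators if they experience intolerable side effects".
- **Leaving (Adverse Events Collection).** "Adverse events that may cause termination or dropout of a subject include hypoglycemia, lactic acidosis, and severe gastrointestinal effects". Events are graded and tabulated, but "no active monitoring for adverse events is planned", and no comparison of events by treatment is described.
- **Dose order (Study Design).** Treatment order is randomised, except that "the 250 mg, 500 mg, 750 mg, and 1,000 mg blocks will always occur in order, smallest to largest".
- **Hypotheses (Primary and Secondary Objectives).** Aim 1 expects similar satisfaction on drug and placebo. A secondary hypothesis is that "scores on a gastrointestinal symptom questionnaire are not significantly different between placebo and intervention periods".

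The plan defines no analysis set for aim 1, no rule for a block cut short, and no method for missing blocks.

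**The concern.** Every participant has a history of metformin intolerance, so stopping for side effects is foreseeable. The reason for leaving is also the thing being measured. A patient who leaves partway through a metformin block contributes placebo scores and lower-dose metformin scores, but not the block that drove the patient out and none of the higher doses. The patients who tolerate metformin contribute everything.

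If some patients are reproducibly intolerant, what remains is tilted toward no difference, which is the answer aim 1 hypothesises. Whether intolerance is reproducible or subjective is the question the trial sets itself, so losing the reproducible cases weakens the answer where it matters most. A score not taken at the time cannot be recovered later.

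**Working it through.** **The plan's own figures.** Lehr's rule gives 16/d² = 16/1² = 16. Going from 16 to 20 implies a dropout allowance of 1 − 16/20 = 20%. Both figures reproduce. This allowance protects precision and has no bearing on which blocks are missing.

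**Simplest case.** Suppose 4 of 20 patients worsen by 2 SD on metformin and leave unscored, and the other 16 have no effect. The true mean difference is 4 × 2/20 = 0.40 SD. The 16 scored patients show 0.

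**Simulation.** The documents give none of these inputs, so all are assumptions:
- 20 patients, 8 alternating blocks, within-patient SD 1, worsening counted as positive.
- A fixed number of intolerant patients (4, 6 or 8), with worsening proportional to added dose.
- A patient stops when a block's score exceeds a cut of 2.5 or 3 SD.
- The analysis is a one-sample t-test on each patient's mean metformin-minus-placebo score, using patients with at least one score in each condition.

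The mean dose fraction is (0.25 + 0.50 + 0.75 + 1.00)/4 = 0.625. With 4 of 20 intolerant and 4 SD at 1,000 mg, the full difference is 4/20 × 4 × 0.625 = 0.50 SD.

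Estimated difference (SD) at a cut of 3 SD:

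| Intolerant; worsening at 1,000 mg | All scored | Half of stoppers leave unscored | All leave unscored | All leave, scored at stop |
|---|---|---|---|---|
| 4 of 20; 4 SD | 0.50 | 0.39 | 0.28 | 0.44 |
| 6 of 20; 4 SD | 0.75 | 0.59 | 0.42 | 0.66 |
| 8 of 20; 3 SD | 0.75 | 0.64 | 0.52 | 0.72 |

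From these rounded figures, the loss when all leave unscored is 0.22/0.50 = 44%, 0.33/0.75 = 44% and 0.23/0.75 = 31%. Over all 12 settings with 3 or 4 SD, it is 31–57% if all leave unscored and 16–28% if half do. It is 0% if every stopper stays and is scored.

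**Smaller effects** (8 of 20 intolerant, all leave unscored):
- 2 SD at 1,000 mg: about 15% lost at a cut of 3 SD, and 29–30% at 2.5 SD.
- 1 SD at 1,000 mg: about 5–6% lost at a cut of 3 SD, and 10–15% at 2.5 SD.

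If all 20 patients are affected with a mean effect of 1.0 SD, the plan's design difference, about 10% is lost at a cut of 3 SD and power stays near 100%.

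**Over-enrolment.** In the first setting of the table, with the same 20% intolerant, enrolling 40 instead of 20 still gives 0.28 against 0.50 SD.

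**No true effect.** All rules give a difference within 0.002 SD of zero, with P(p<0.05) of 0.043–0.050.

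**A different leaving mechanism.** Here 40% of patients are affected by a mean of 1 SD, and affected patients leave at random with a chance that rises with dose, whatever the block's own score. With a mean chance of 20% per metformin block, the difference falls from 0.400 to 0.295 SD (26% lost). With 40%, it falls from 0.407 to 0.230 SD (43% lost). The direction is the same, and the size depends heavily on the leaving rate.

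**The case against.** The strongest reply is textual. Patients are told to stop the medication and make contact, not to leave the study, and the end-of-period questionnaires carry no condition of being on drug. On the ordinary reading, a patient who stops but stays is scored at day 14. That stands: a reader might infer that every stopper goes unscored, and the documents do not support it. The bias needs actual departure. Adverse Events Collection allows for departure after severe effects but gives no rate.

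Second, the large losses come from settings with 3–4 SD worsening at the top dose, where affected patients stop almost surely (3.9 stops with 4 intolerant) and the score that triggers leaving is the one that goes missing. This also stands as to size, and it is why smaller effects are shown. It does not change the direction, which holds under the random-leaving model too.

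Third, intolerance can show elsewhere: in the adherence comparison, the graded adverse events, and tolerance at 6 months under aim 2. These make a misleading conclusion less likely. They do not repair the satisfaction or gastrointestinal comparison.

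Fourth, a reader might infer that a non-significant result would be caused by the missing blocks. That goes too far. With 4 of 20 intolerant at 4 SD, P(p<0.05) is only 32% with every block scored, so about 68% of such trials would be non-significant anyway; unscored leaving lowers 32% to 18%. The effect on detection is larger elsewhere: 75% falls to 38% with 6 of 20 at 4 SD, and 63% to 51% with 8 of 20 at 2 SD (cut 3 SD). The absence of a margin for similarity is a separate and larger issue.

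**Conclusion.** The point holds in a limited form. As written, the plan leaves a mid-block leaver without a score for that block or for any higher dose, and enrolling 20 for 16 does not address this. If metformin truly worsens tolerability in some patients, aim 1 is biased toward the hypothesised result.

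If all stoppers leave unscored, the threshold simulation loses roughly 5–30% of the difference with worsening of 1–2 SD at 1,000 mg, and roughly 30–57% with 3–4 SD. The loss shrinks as more stoppers stay and are scored, and it is zero if nobody leaves or there is no true effect. These sizes rest on assumed effects and leaving rules. The documents establish the gap and, given a true effect, the direction of the bias. They do not establish that departures will be common or that the trial's result will be wrong. This is a cheap improvement worth making, not a flaw that invalidates the design.

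**What to change.** 1. **Procedures, one sentence.** A patient who stops study drug or leaves because of an adverse event completes that block's existing questionnaires at the stop, before unblinding. Those who stay also complete the scheduled end-of-period questionnaires.
2. **Analysis, one short paragraph.** Aim 1 satisfaction and gastrointestinal comparisons include all patients with at least one metformin and one placebo score, using the stop score when the patient leaves. Adverse-event stops are reported descriptively by treatment and added dose.
3. **Optional.** An analysis without stop scores, and a bound that gives the worst score to a block ended by an adverse event without a questionnaire. If the worst score is 5 SD, this overshoots by about 2–15% in the 3–4 SD settings, so it serves only as a bound.

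No new instrument is needed, and patients are already asked to contact the investigators when they stop.

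The costs and limits are:
- A symptomatic patient is asked to fill in a questionnaire.
- A stop score reflects less than two weeks of exposure and may catch peak symptoms. If it runs 0.5 SD worse than the day-14 score, the estimate in the 3–4 SD settings ranges from 15% too small to 1% too large.
- Later, higher-dose blocks stay missing, so about 0–22% of the difference is still lost.
- A patient who leaves in the first block has no within-patient comparator.
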